4.3. PATIENT GLOBAL IMPRESSION OF CHANGE (PGIC) – MUSCLE SYMPTOMS AND FATIGUE SYMPTOMS

The subject is asked to rate both their change in PMM muscle symptoms and change in PMM fatigue symptoms at Week 24 (or, if applicable, the Early Termination visit). The PGIC has a 7-point scale from 'Very Much Improved' to 'Very Much Worse'. This will be converted to a numeric scale from 3 (very much improved) to -3 (very much worse); hence a value of 0 will mean no change. These scores are exploratory endpoints.

Additionally, responder endpoints for both muscle symptoms and fatigue symptoms will be analysed, which is defined as a response of ‘Very Much Improved’ or ‘Moderately Improved’. The PGIC responder endpoints are also exploratory endpoints.

4.4. 30 SECOND SIT TO STAND TEST (30STS)

The purpose of the 30 second sit-to-stand test (30STS) exploratory endpoint is to assess leg strength and endurance. Subjects are required to sit and rise to a full standing position as many times as they can in 30 seconds. A subject should only conduct the test if they are able to stand without using their arms to assist them out of the chair. A score of zero and a reason for not completing the test will be noted in the electronic Case Report Form (eCRF) in these circumstances.

Subjects will perform the test at Baseline, Week 12 and Week 24 visits. If applicable, the test will also be performed at the Early Termination visit.

For each visit changes from baseline will be calculated.

4.5. PEDOMETER STEP COUNT

Subjects are provided with a pedometer and access to an eDiary. Sites will train the subject on how and when to use the pedometer and to record their daily step count. Daily step counts should be recorded in the eDiary for 14 days during the screening period and for 7 consecutive days within a 2-week window before each study visit (Weeks 4, 12, 18 and 24).

Note, collection of eDiary data is optional and only subjects who are able and willing to use a pedometer and record data in the eDiary will be included in the analyses. In addition, the Belgium site did not allow collection of pedometer data. Therefore, subjects that have no eDiary data collected will be excluded.

If the subject forgets to reset the pedometer at the start of the day, then the step count from the previous day will be subtracted. If the data for the previous day is missing or if the step count for the previous day is greater than the step count recorded on this day, suggesting the pedometer was reset part way through the collection, then the value will not be used and will be set to missing.

Two endpoints will be calculated; the median daily step count and the average daily step count over the non-missing eDiary data collected for the visit period. The average accounts for the whole week and takes into account changes in the daily activity patterns of subjects, whilst the median accounts for extreme values that may not represent the subject’s activity (e.g., forgetting to wear the pedometer).

Ideally 7 consecutive days of step count data will be used to calculate these step count endpoints for each visit; however, if 7 consecutive days are not available then a minimum

of 4 days of data will be required for each visit. If there are 3 days or fewer of diary data for a visit, then the step count endpoints will be excluded from the analyses and identified in the data listing. The baseline will be calculated over the last 7 consecutive days of recordings prior to Day 1. If there are no 7 consecutive day periods with recordings, then the latest 7-day period with the most amount of completed days in the baseline period will be used. For post baseline visits (except Week 4) all diary data collected in the analysis visit window will be considered (refer to [Section 8.4](#)) and the 7 consecutive days finishing closest to the target visit date will be used. For Week 4 the lower limit of the analysis window will be widened to allow for the fact that the diary opens 2 weeks prior to the target visit date. If there are no 7 consecutive day periods with recordings, then the 7-day period with the most amount of completed days will be used.

For each visit changes from baseline and percent changes from baseline will be calculated.

4.6. PATIENT GLOBAL IMPRESSION OF SEVERITY (PGIS) SCORE - MUSCLE SYMPTOMS AND FATIGUE SYMPTOMS

At Screening, Baseline, Week 4, Week 12, Week 18 and Week 24 visits, the subject will be asked to rate the severity of their PMM for muscle symptoms and for PMM fatigue symptoms over the past 7 days. If applicable, they will be asked the questions at the Early Termination visit. Both the PGIS muscle symptoms and PGIS fatigue symptoms are exploratory endpoints.

The scale has 5 levels from ‘Absent’ to ‘Very Severe’.

For each visit changes from baseline will be calculated for the two symptom scores.

4.7. MODIFIED FATIGUE IMPACT SCALE (MFIS)

The MFIS is a detailed tool that is completed by the subject. Scoring is simple, the score reflects functional limitation due to fatigue experienced within the previous 7 days rather than a measure of the current level of fatigue. The MFIS will be used at Screening, Baseline, Week 4, Week 12, Week 18 and Week 24 visits. If applicable, the test will also be performed at the Early Termination visit.

During the conduct of the study, it has been identified that there was a translation error for the Netherlands site (site 2301) questionnaire, which incorrectly stated the recall period of 4 weeks instead of 7 days. This affected several subjects at the site for some visits. As a result, a sensitivity analysis will be performed excluding data from subjects at this site.

There are 21 items, each of which is scored 0 (never) to 4 (almost always), providing a continuous scale of 0–84. It is composed of three subscales that describe the impact of fatigue on physical (9 items), cognitive (10 items) and psychosocial functioning (2 items). Physical functioning reflects motivation, effort, stamina and coordination. Cognitive

functioning concerns concentration, memory, thinking and organization of thoughts. Psychosocial functioning describes the impact of fatigue upon isolation, emotions, workload and coping. All items are scaled so that a higher score indicates a greater impact of fatigue. The below table shows how to calculate the 3 subscales and the total score:

Subscale	Items	Range
Physical	4+6+7+10+13+14+17+20+21	0 – 36
Cognitive	1+2+3+5+11+12+15+16+18+19	0 – 40
Psychosocial	8+9	0 – 8
Total Score	Physical + cognitive + psychosocial subscales	0 – 84

There is no recommended methodology for handling missing component scores for this questionnaire, however, to utilize all available data the following is proposed:

- if 50% or more of the component scores are missing, then the subscale will not be derived and as a result the total score will not be derived. In this situation the subscale(s) with $\geq 50\%$ missing component scores and the total score will be considered missing, and handled using the same methods described in [Section 8.3.1](#) for other MFIS missing data
- if less than 50% of the component scores are missing then the average, rounded up to the nearest integer, of the non-missing scores for the subscale will be used to impute each missing value

For each visit changes from baseline and percent changes from baseline will be calculated for each of the sub-scale scores and the total score. These scores are exploratory endpoints.

4.8. 36 ITEM SHORT FORM SURVEY (SF-36)

The SF-36 version 2.0 Health Survey asks questions, with a one week recall period, which cover 8 health concepts: physical functioning, bodily pain, role limitations due to physical health problems, role limitations due to personal or emotional problems, mental health, social functioning, vitality (referred to in the protocol as energy/fatigue) and general health perceptions. It also includes a single item that provides an indication of perceived change in health. If mavodelpar is effective greater improvements are anticipated with vitality than the other health concepts.

The SF-36 will be used at Baseline, Week 4, Week 12, Week 18 and Week 24 visits. If applicable, the test will also be performed at the Early Termination visit.

All scale scores are exploratory endpoints and will be derived using QualityMetric Health Outcomes Scoring Software 5.0. This software generates standardized scores in accordance with the standards set by the developers of the survey. All items are scored so

that a high score defines a more favourable health state. In addition, each item is scored on a 0 to 100 range.

For each visit changes from baseline will be calculated for each health concept scale.

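### One blank Psychosocial item counts as 50% missing, so the MFIS Total is not derived with 20 of 21 items answered, although a Total with 8 blanks elsewhere can be derived

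*SAP*

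**What the plan says.** SAP section 4.7 describes the instrument: "There are 21 items, each of which is scored 0 (never) to 4 (almost always), providing a continuous scale of 0–84". The items fall into three subscales, "physical (9 items), cognitive (10 items) and psychosocial functioning (2 items"), with items 8 and 9 forming the Psychosocial subscale. The Total is defined as "Physical + cognitive + psychosocial subscales".

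The section notes that no missing-item method is recommended for this questionnaire and offers its own, introduced with the words "to utilize all available data the following is proposed". It has two parts:

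- Upper part: this applies to a subscale with at least half of its items blank, the limit itself included. The stated consequence reaches beyond that subscale: "then the subscale will not be derived and as a result the total score will not be derived". The subscale and the Total are then treated as missing under section 8.3.1.
- Lower part: "if less than 50% of the component scores are missing then the average, rounded up to the nearest integer, of the non-missing scores" in the subscale replaces each blank.

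There is no exception for the two-item subscale and no separate rule for the Total based on all 21 items. Protocol section 7.1.12 gives the scoring but no missing-item rule. On status, SAP section 4.7 says: "These scores are exploratory endpoints".

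**The concern.** A percentage threshold behaves differently on a short scale. With nine or ten items, 50% tolerates four blanks. With two items it tolerates none, because one blank already reaches the limit. The lower part of the rule, which fills blanks from the answered items, can therefore never operate on items 8 and 9. Because the Total requires all three subscales, this carries over to the Total: an almost complete form can yield none, while a much less complete form yields one.

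At stake is the completeness of the MFIS Total, which has its own MMRM, summaries and shift tables (SAP 10.3.5) and is plotted against the 12MWD (SAP 10.4). There is also a smaller effect on baseline. If the Day 1 Total is not derived, SAP 8.2 and 8.3 allow the Screening value to serve instead. The Total's change is then measured from a visit up to 8 weeks before dosing, while the same subject's Physical and Cognitive changes are measured from Day 1.

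**Working it through.** **Inputs (SAP 4.7).** Physical 9 items, Cognitive 10, Psychosocial 2; each item scored 0 to 4.

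**Reproducing the stated ranges.** 4 × 9 = 36, 4 × 10 = 40, 4 × 2 = 8 and 4 × 21 = 84. These match the SAP's table, and the three item lists cover items 1 to 21 once each.

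**Where the threshold falls.**

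| Subscale | Most blanks still derived | First count not derived |
|---|---|---|
| Physical (9) | 4 (44.4%) | 5 (55.6%) |
| Cognitive (10) | 4 (40.0%) | 5 (50.0%) |
| Psychosocial (2) | 0 (0%) | 1 (50.0%) |

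The most blanks with a Total still derived is 4 + 4 + 0 = 8 of 21, leaving 13 answered. One blank in item 8 or 9, with 20 of 21 answered (95.2%), gives no Total.

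**Illustrative frequency.** The documents give no item non-response rate. Assume each item is blank independently with probability p = 0.5%, 1% or 2%.

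- Total lost through Psychosocial at one visit: L = 1 − (1 − p)².
- Loss through Physical or Cognitive: P(Bin(9, p) ≥ 5) and P(Bin(10, p) ≥ 5).
- Day 1 and Screening Totals both lost: L².
- Subject loses at least one Total among Weeks 4, 12, 18 and 24, or has no usable baseline Total: 1 − (1 − L)⁴ × (1 − L²).

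| p | L | Physical + Cognitive loss | L² | At least one Total lost |
|---|---|---|---|---|
| 0.5% | 1.0% | under 0.00001% | 0.01% | 3.9% |
| 1% | 2.0% | under 0.00001% | 0.04% | 7.8% |
| 2% | 4.0% | 0.00011% | 0.16% | 15.1% |

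For p = 1%: L = 1 − 0.99² = 0.0199, and 1 − (0.9801)⁴ × (1 − 0.000396) = 1 − 0.9227 × 0.9996 = 0.078. If all 200 planned subjects returned a form, L corresponds to about 2, 4 or 8 Totals lost at a visit. Practically all of the loss comes through the two-item subscale.

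**What the rule saves.** With no item-level imputation, any blank would lose the Total: 1 − (1 − p)²¹ = 10.0%, 19.0% or 34.6%. Under the rule the loss is 1.0%, 2.0% or 4.0%, so it recovers nearly 90% of the Totals that would otherwise be lost.

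**Dependence between items 8 and 9.** Independence gives close to the largest loss. If the two items were always blank together, L would fall to p (1.0% at p = 1%), and filling one from the other would recover nothing.

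**The case against.** The strongest reply is that the rule largely works and the consequences are slight.

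- *The rule serves its aim.* As shown above, it recovers nearly 90% of Totals that a no-imputation rule would lose. A reader might infer that it does the opposite of using all available data. The documents do not support that: for 19 of the 21 items it does what it says, and it falls short only for items 8 and 9.
- *Subjects are not lost.* A reader might infer that a missing Day 1 Total removes the subject from the Total MMRM, because baseline is a covariate. SAP 8.2 defines baseline as the last non-missing pre-dose assessment, SAP 8.3 permits Screening values as a substitute, and the MFIS is collected at Screening. The subject drops out only if both Totals are missing, which is 0.01% to 0.16% on the assumed rates. A lost post-baseline Total is one missing visit in an MMRM that keeps the subject's other visits.
- *The 8-blank form is a rare extreme.* It requires exactly four Physical and four Cognitive blanks with both Psychosocial items answered; other patterns of eight lose the Total. It shows what the rule accepts, not what will often occur.
- *Filling one item from one other item is a judgement.* Item 8 concerns motivation for social activities and item 9 concerns doing things away from home (Protocol Appendix 2). The Total would also no longer equal the sum of the reported subscales.

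The first three points limit the concern to its true size. The fourth is a fair cost, but a small one: at most 4 of 84 points would be imputed, where the rule already accepts up to 8 imputed items, or 32 of 84 points. None of them removes the gap. The 50% cannot be read as applying to all 21 items, because the text ties it to the subscale.

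**Conclusion.** The point holds as a minor gap in a scoring rule. It follows from the SAP's own item counts and from the inclusive threshold, and no other section makes an exception. Its size depends on assumed, independent item non-response: 1.0% to 4.0% of Totals per visit for rates of 0.5% to 2%, and about 3.9% to 15.1% of subjects with at least one Total lost after the Screening substitution. These percentages describe lost visit values, not lost subjects. No bias in the treatment comparison is shown.

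The MFIS Total is exploratory. The fixed testing sequence in SAP 8.2 contains only the 12MWD and the PROMIS T-score, so the primary and secondary tests are unaffected. One blank Psychosocial item also leaves the Physical and Cognitive subscales untouched. This is a cheap improvement, not a threat to the trial's conclusions.

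**What to change.** Add to SAP section 4.7, before database lock: the Total is derived when the Physical and Cognitive subscales each have fewer than 50% of their items missing and at least one Psychosocial item is answered; a single blank Psychosocial item takes the value of the answered one, for the Total only. The Psychosocial subscale itself stays missing under the current rule. Add a note that such a Total includes an imputed Psychosocial item and is not the sum of the reported subscales.

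On the illustrative assumptions, loss through Psychosocial then needs both items blank: p² = 0.0025%, 0.01% or 0.04% of Totals per visit, in place of 1.0%, 2.0% or 4.0%.

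The cost is a sentence, a note and a small programming change. The downside is that one item, worth at most 4 of 84 points, is filled from its pair.

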Categorical shift tables of change from baseline showing improvement (at least a 4-point decrease in score), no change (less than a 4-point change in either direction) or worsening (at least a 4-point increase in score) at each visit will be summarized. The table will include categories for withdrawn and missing. Percentages will not be presented for the withdrawn and missing rows, and the percentages presented will use the number of non-missing values as the denominator. In addition, to account for subjects at the extreme ends

of the scale, the shift table will also include the percent improving or worsening based on those subjects who have the potential to improve or worsen respectively.

As a sensitivity analysis the main analysis will be repeated excluding subjects from the Netherlands site to assess if there was an impact due to the incorrect recall period being included on the questionnaire for subjects at this site.

Total and sub-scale scores and changes from baseline will be listed separately from the raw data.

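### The MFIS item-imputation rule rounds the subscale mean up, so prorated Physical, Cognitive and Total scores shift toward worse fatigue by about 0.4 points per missing item on average

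*SAP*

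**What the plan says.** SAP 4.7 describes the instrument: "There are 21 items, each of which is scored 0 (never) to 4 (almost always"). The subscales describe the impact of "fatigue on physical (9 items), cognitive (10 items) and psychosocial functioning (2 items"). On direction it says: "All items are scaled so that a higher score indicates a greater impact of fatigue".

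For partly completed forms the SAP states: "There is no recommended methodology for handling missing component scores for this questionnaire". It then proposes two rules of its own:

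- "if 50% or more of the component scores are missing, then the subscale will not be derived", and the total is then not derived either.
- "if less than 50% of the component scores are missing then the average, rounded up to the nearest integer, of the non-missing scores" of that subscale is used to fill each missing item.

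No reason is given for the rounding. On status, SAP 4.7 says: "These scores are exploratory endpoints". SAP 10.3.5 analyses changes from baseline with an MMRM, using baseline MFIS as a continuous covariate. It also tabulates "improvement (at least a 4-point decrease in score"), with the mirror-image definition of worsening.

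**The concern.** The mean of the answered items already estimates a missing item. Taking it up to the next integer adds an amount that the answered items do not support, always in the same direction.

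The addition grows with the number of missing items. It enters a change score with opposite signs: an incomplete Baseline form creates some false improvement, and an incomplete later form creates some false worsening. The affected values feed the MMRM, the percent changes from baseline and the 4-point shift tables. The only MFIS-specific sensitivity analysis, which leaves out the Netherlands site, does not address it.

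The wording is also loose. A programmer could read it as a strict round-up or as ordinary rounding, and the two can give clearly different scores for the same form.

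**Working it through.** The documents give no figure for the size of this shift, so there is none to reproduce.

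**Inputs (SAP 4.7).** Items are integers from 0 to 4. Subscale sizes are 9, 10 and 2. Filling applies when fewer than half the items are missing. That means 1 to 4 missing of 9, or 1 to 4 missing of 10. One missing of 2 is already 50%, so Psychosocial is never prorated.

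**Formula.** Let m items be answered, with sum S. The shift per filled item is ceil(S/m) − S/m. It runs from 0 (S/m an integer) to (m−1)/m. If the remainder of S after division by m is evenly spread over 0 to m−1, the average is (m−1)/(2m). Multiplying by the number missing gives the shift in the subscale.

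| Subscale | Missing | m | Average per item | Average in subscale | Maximum in subscale |
|---|---|---|---|---|---|
| Physical | 1 | 8 | 7/16 = 0.438 | 0.44 | 7/8 = 0.88 |
| Physical | 2 | 7 | 6/14 = 0.429 | 0.86 | 2 × 6/7 = 1.71 |
| Physical | 3 | 6 | 5/12 = 0.417 | 1.25 | 3 × 5/6 = 2.50 |
| Physical | 4 | 5 | 4/10 = 0.400 | 1.60 | 4 × 4/5 = 3.20 |
| Cognitive | 1 | 9 | 8/18 = 0.444 | 0.44 | 8/9 = 0.89 |
| Cognitive | 2 | 8 | 7/16 = 0.438 | 0.88 | 2 × 7/8 = 1.75 |
| Cognitive | 3 | 7 | 6/14 = 0.429 | 1.29 | 3 × 6/7 = 2.57 |
| Cognitive | 4 | 6 | 5/12 = 0.417 | 1.67 | 4 × 5/6 = 3.33 |

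**Sensitivity to the item distribution.** The documents give no distribution, so these are assumptions.

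- Independent items without a strong floor (exact convolution): 0.40 to 0.49 per item.
- A strong floor distribution: 0.43 to 0.62.
- Items correlated within a subject (simulation): 0.32 to 0.44.

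**Share of prorated scores that do not move.** With evenly spread remainders this is 1/m, or 11% (m = 9) to 20% (m = 5). It reaches about 37% in the assumed correlated cases.

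**If ordinary rounding (halves up) is meant.** With evenly spread remainders the average shift is 0 for odd m and 1/(2m) for even m: 1/16 = 0.06 and 1/12 = 0.08. In the strong-floor case it turns slightly negative (−0.04 to −0.16).

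**Worked example.** Five Physical items are answered and sum to 11, so the mean is 2.2 and four items are missing.

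- Unrounded: 11 + 4 × 2.2 = 19.8
- Rounded up: 11 + 4 × 3 = 23
- Ordinary rounding: 11 + 4 × 2 = 19

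The round-up adds 3.2 points. The two readings of the sentence differ by 4 points, which equals the shift-table threshold.

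**Total score.** With four items missing in both prorated subscales, the average shift is 1.60 + 1.67 = 3.27 and the maximum is 3.20 + 3.33 = 6.53.

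**The case against.** The strongest reply is that the consequence for the trial is small.

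- The same rule applies in both arms and at every visit of a randomized, double-blind trial. The shift therefore largely cancels in the treatment difference unless item missingness differs by arm or visit. This stands.
- All MFIS scores are exploratory (SAP 3.2.5, 4.7 and 14). The fixed sequence in SAP 8.2 covers only the 12-minute walk distance and the PROMIS T-score, and neither uses this rule. This stands.
- The larger figures need four blank items in one subscale. With one blank item the average is about 0.44 on a 0–36 or 0–40 scale. A Physical or Cognitive shift stays below 4 points even at its maximum, so rounding alone cannot turn no change in those subscales into improved or worse. It can only tip borderline cases. This stands; only the Total, in the extreme case, can exceed 4 from rounding alone.
- Ordinary rounding may have been intended. That is possible, but the sentence then still needs correcting.
- Integer fills keep items on their response scale, and no standard method exists. This supports rounding to an integer, not rounding up. SAP 4.7 calls the scale continuous, and SAP 4.9 averages the answered Brief Pain Inventory severity items without rounding.

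A reader might infer that every prorated score is biased. It is not: scores whose answered items average to an integer do not move, and Psychosocial is never prorated. A reader might also infer a biased treatment effect. The documents do not show that, because they give no item-missingness rate by arm or visit.

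**Conclusion.** The point holds as a minor defect in a scoring rule. On the plain reading, prorated Physical, Cognitive and Total scores are never lowered and usually raised toward worse fatigue. The average is about 0.4 points per missing item, with a range of roughly 0.3 to 0.6 that depends on assumed item distributions. At four missing items in a subscale the shift averages 1.6 to 1.7 points and can be as large as 3.2 to 3.3.

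Individual scores and some borderline shift-table classifications can therefore be wrong. Within a subject the shift cancels on average only if similar numbers of items are missing at both visits. The effect on the REN001-minus-placebo difference cannot be computed and is probably small. No confirmatory result depends on it. This is a free improvement, not a threat to the trial's conclusions.

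**What to change.** In SAP 4.7, delete the rounding clause and fill each missing item with the unrounded mean of the answered items in that subscale. Equivalently, the subscale score is the mean of the answered items times the number of items. Keep the 50% rule as it stands.

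This removes both the upward shift and the ambiguity about which rounding is meant. It changes one phrase and one line of scoring code, needs no new data, and fits the SAP's own condition that amendments are made before database lock (SAP 2).
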